**6 ANALYSIS POPULATION**

Analyses for the endpoints will be performed using the intent-to-treat (ITT) population. The ITT population will consist of all subjects enrolled in the study, excluding roll-ins, and for whom a device insertion was attempted, regardless of the treatment actually received.

The per-protocol analysis population is defined as a sub-group of the ITT population consisting of subjects without protocol deviations that could possibly affect the primary endpoints. Primary endpoint analysis using this population is supportive in nature.

**7 RANDOMIZATION**

This is a non-randomized, single arm study.

## 8 STATISTICAL METHODS OF ANALYSIS

### 8.1 General Considerations

Except where otherwise specified, the following general principles apply to the planned statistical analyses. All descriptive statistical analyses will be performed using SAS version 9.4 or higher, unless otherwise noted (SAS Institute Inc., Cary, NC) or other widely accepted statistical or graphical software as required. Derived variables will be independently verified by an independent programmer / statistician.

In general, for categorical variables, the numerator, denominator, rate (%) and exact 95% CI will be calculated. For continuous variables, the median, mean, standard deviation, interquartile range, number of observations, minimum and maximum values, and 95% CI, as appropriate, will be presented.

For each parameter, the baseline value will be defined as the last non-missing value collected at the time closest to but before treatment with the investigational device.

Statistical tests of the primary endpoints will be performed at the one-sided 0.05 significance level.

### 8.2 Subject Disposition

Subject accountability will be summarized in tabular form.

### 8.3 Subject Demographics and Baseline Variables

All baseline variables will be summarized using descriptive statistics. Continuous variables will be summarized using the mean, standard deviation, N, minimum, and maximum. Categorical variables will be summarized as frequencies and proportions. Baseline variables for all enrolled subjects will be summarized, however roll-in subjects will be summarized separately.

### 8.4 Analyses of Safety Endpoints

#### 8.4.1 Primary Safety Endpoint Analysis

The primary safety endpoint is the occurrence rate of device or procedure-related complications associated with transradial artery access through the time of hospital discharge.

The safety hypothesis being tested is:

$H_0: \pi \geq 0.07$

Vs

$H_a: \pi < 0.07$

where  $\pi$  is the proportion of subjects experiencing a radial access related complication.

A one-sided upper exact 95% CI for device or procedure-related radial artery complications rate will be calculated using the Clopper-Pearson method. The upper bound will be compared to the performance goal of 7%. If the upper bound is less than the performance goal, then this endpoint will have been successfully achieved.

Even though some subjects may contribute bilateral lesions, the safety analysis will be analyzed on a per subject basis.

The same analysis will be completed on the per-protocol analysis population if that population is different from the ITT population.

#### **8.4.2 Secondary Safety Endpoint Analysis**

Secondary safety endpoints will be summarized using the statistical methods described in section 8.1. All secondary safety endpoints will be summarized on a per subject basis. In particular, each of the rates outlined in section 4.1 will be estimated and presented with a two-sided 95% confidence interval that is calculated using the Clopper-Pearson method in addition to the other descriptive statistics.

No formal hypothesis testing will be done on the secondary safety endpoints.

### **8.5 Analyses of Effectiveness Endpoints**

#### **8.5.1 Primary Effectiveness Endpoint Analysis**

The primary efficacy endpoint is technical success at the conclusion of the index procedure defined as successful insertion of the S.M.A.R.T. RADIANT™ Vascular Stent System through the vasculature, successful deployment of the study device (S.M.A.R.T.™ stent) at the intended location, and successful withdrawal of the delivery system without conversion to femoral access.

The hypothesis being tested is:

$H_0: \pi \leq 0.93$

Vs

$H_a: \pi > 0.93$

where  $\pi$  is the proportion of limbs successfully treated with one or more S.M.A.R.T. RADIANT™ Vascular Stent Systems.

A one-sided lower exact 95% CI for technical success rate will be calculated using the Clopper-Pearson method. The lower bound will be compared to the performance goal of 93%. If the lower bound is greater than the performance goal then this endpoint will have been successfully achieved.

This analysis will be done on a per limb basis since some subjects enrolled in the trial have bilateral lesions. Each lesion can be treated with up to two stents. In the case that two stents are used, success is based on successful insertion of each of the S.M.A.R.T. RADIANT™ Vascular Stent System through the radial artery, successful deployment of both stents at the intended location and the successful withdrawal of both systems with no conversion to femoral access. While some subjects will present with bilateral lesions, the actual number of those subjects will be small. As such, each limb will be considered an independent observation for the purpose of analysis of this endpoint.

The same analysis will be completed on the per-protocol analysis population if that population is different from the ITT population.

### **8.5.2 Secondary Effectiveness Endpoint Analysis**

The secondary endpoint of technical success of the BRITE TIP RADIANT™ Guiding Sheath will be summarized on a per subject basis since the guiding sheath would not be completely removed between lesion treatments of a bilateral subject. The number of successfully inserted BRITE TIP RADIANT guiding sheaths will be counted and divided by the number of BRITE TIP RADIANT guiding sheaths with attempted insertions to estimate the technical success. A two-sided 95% exact confidence interval will be constructed about the technical success rate. The confidence interval will be calculated using the Clopper-Pearson method.

Procedural success of the SABERX RADIANT™ PTA Balloon Catheter will be summarized on a per limb basis. In the case where pre-dilation and post-dilatation are performed and/or more than one SABERX RADIANT balloon was used to treat a lesion, each device must be successfully inserted into the peripheral vasculature through the radial artery, successfully inflated and deflated, and successful withdrawn with the achievement of a final residual diameter stenosis of < 30% for the treated lesion. The number of successful procedures using the SABERX RADIANT™ PTA Balloon Catheter will be calculated for each limb. A two-sided 95% exact confidence interval will be constructed about the procedural success rate. The confidence interval will be calculated using the Clopper-Pearson method.

No formal hypothesis testing will be done on the secondary effectiveness endpoints.

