13.6 Device Deficiencies

A device deficiency is any inadequacy in the identity, quality, durability, reliability, safety or performance of an investigational device, including device malfunction, use errors or inadequacy in information supplied by the manufacturer.

- A device malfunction is considered a failure of a device to meet any of its performance specifications or otherwise perform as intended. Performance specifications include all claims made in the Instructions for Use (IFU)/Investigator's Brochure (IB)/clinical study protocol.

In the event of a device deficiency, detailed information on the product, circumstances of the deficiency as well as any complications and their management will be collected and reported.

Though subjects are considered enrolled only from the time they are confirmed to qualify for study participation according to the eligibility criteria (i.e., upon completion of angiography), all device deficiencies for all enrolled subjects, including those from the "roll-in" cohort of the study, will be reported retroactive to the initial use or handling of a study device until their exit from the study (i.e., point of study completion or premature discontinuation).

The Investigator must report all new device deficiencies or changes to previously-reported device deficiencies (based on any new findings), with whatever information is available at the time, to the sponsor and/or designee by any acceptable method as communicated by them, within 24 hours or one working day of first awareness of the event by the study team at the institution and provide any additional information as required by the sponsor/designee. If the event is not reported through the EDC system within this time

RADIANTY / P21-7701

Version: 7.0 / March 21, 2023

period, it must be done so as soon as possible. If applicable, the Investigator must make arrangements for the safe return of any malfunctioned, damaged, and/or unused investigational devices in accordance with the instructions provided by the sponsor.

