### 4.2 Effectiveness Endpoints

The primary efficacy endpoint is technical success at the conclusion of the index procedure, defined as successful insertion of the S.M.A.R.T. RADIANT™ Vascular Stent System into the peripheral vasculature through the radial artery, successful deployment of the study device (S.M.A.R.T.™ stent) at the intended location, and successful withdrawal of the delivery system without conversion from radial to femoral artery access.

The secondary effectiveness endpoints include:

- Technical success associated with use of the BRITE TIP RADIANT™ Guiding Sheath, defined as successful insertion of the device into the peripheral vasculature through the radial artery (allowing for introduction of interventional and/or diagnostic devices) and successful withdrawal of the device.
- Procedural success associated with use of the SABERX RADIANT™ PTA Balloon Catheter for pre-dilation and/or post-deployment stent dilatation (whenever applicable), defined as successful insertion of the device into the peripheral vasculature through the radial artery, successful inflation and deflation of the balloon,

successful withdrawal of the device, and achievement of a final residual diameter stenosis of < 30% at the conclusion of the index procedure.

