## 12 PLANNED TESTS AND EXPECTED RESULTS

Planned a priori analyses and expected results, where applicable, are shown in Table 1.

Variable	Analysis	Expected Result	Cohort			
			ITT	PP	Non-Roll-in	Roll-in
Technical Success (Primary) Non-Roll-in Subjects Only	One-Sided Lower Exact 95% CI	Confidence Interval does not include 93%	X		X	
Technical Success (Primary) Roll-in Subjects Only	One-Sided Lower Exact 95% CI	Exploratory	X			X
Technical Success (Primary) Non-Roll-in, Per Protocol Subjects Only	One-Sided Lower Exact 95% CI	Confidence Interval does not include 93%		X	X	
Sensitivity Analysis for Primary Technical Success. Non Roll-in Subjects Only	One-Sided Lower Exact 95% CI	N/A	X		X	
Subgroup analysis for Primary Efficacy Variables by Gender and Lesion Type (Iliac and Femoral/Popliteal)	One-sided Lower Exact 95% Confidence Interval	Confidence Interval Does Not Include 93%			X	X
Major Radial Access Site Complications Attributed to Device or Procedure Through Discharge (Primary) Non-Roll-in Subjects Only	One-Sided Lower Exact 95% CI, w/wo	Confidence Interval Does Not Include 7%	X		X	

Major Radial Access Site Complications Attributed to Device or Procedure Through Discharge (Primary) Roll-in Subjects Only	One-Sided Lower Exact 95% CI	Confidence Interval Does Not Include 7%		X	X	
Major Radial Access Site Complications Attributed to Device or Procedure Through Discharge (Primary) Roll-in Subjects Only	One-Sided Lower Exact 95% CI	Exploratory	X			X
Sensitivity Analysis for Major Radial Access Site Complications Attributed to Device or Procedure Through Discharge (Primary) Non-Roll-in Subjects Only	One-Sided Lower Exact 95% CI, w/wo	N/A	X		X	
Subgroup Analysis for Major Radial Access Site Complications Attributed to Device or Procedure Through Discharge (Primary) by Gender and Lesion Type (Iliac and Femoral/Popliteal)	One-Sided Lower Exact 95% Confidence Interval	Confidence Interval Does Not Include 7%			X	X
Rate of Brite Tip Radianz Guiding Sheath Deficiencies Non-Roll-in Subjects	Two-sided Exact 95% Confidence Interval (one or more per procedure, w/wo)	Exploratory			X	
Rate of Brite Tip Radianz Guiding Sheath Deficiencies Roll-in Subjects	Two-sided Exact 95% Confidence Interval (one or more per procedure, w/wo)	Exploratory				X
Rate of SaberX Radianz PTA Balloon Catheter Deficiencies Non Roll-in Subjects Only	Two-sided Exact 95% Confidence Interval (one or more per procedure, w/wo)	Exploratory			X	

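### SAP 8.5.2 calculates BRITE TIP RADIANT technical success from insertion alone, although the defined endpoint also requires successful withdrawal

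*SAP*

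**What the plan says.** The endpoint is defined in SAP 4.2 and, in the same terms, in Protocol 8.2 and the protocol synopsis. The first condition is insertion: "defined as successful insertion of the device into the peripheral vasculature through the radial artery (allowing for introduction of interventional and/or diagnostic devices". The definition then adds withdrawal: "allowing for introduction of interventional and/or diagnostic devices) and successful withdrawal of the device".

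SAP 8.5.2 gives the calculation: "successfully inserted BRITE TIP RADIANT guiding sheaths will be counted and divided by the number of BRITE TIP RADIANT guiding sheaths with attempted insertions". A two-sided 95% Clopper-Pearson interval is put around the result, and no hypothesis is tested.

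The sentence before the formula gives the unit. The endpoint "will be summarized on a per subject basis since the guiding sheath would not be completely removed between lesion treatments of a bilateral subject". Protocol 14.4.2 states the same unit and gives no formula.

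The next paragraph of SAP 8.5.2 deals with the SABERX RADIANT balloon and does carry withdrawal into the scoring: "each device must be successfully inserted into the peripheral vasculature through the radial artery, successfully inflated and deflated, and successful withdrawn".

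Table 1 in SAP 12 has rows for sheath deficiencies (for example "Rate of Brite Tip Radianz Guiding Sheath Deficiencies Non-Roll-in Subjects") but none for sheath technical success.

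**The concern.** The definition requires two things and the counting rule checks one. A programmer who codes the sentence in SAP 8.5.2 literally will count an inserted sheath as a success even if its withdrawal failed. The definition counts the same sheath as a failure. The formula is therefore blind to one of the two ways of failing that the endpoint was written to capture, and the error always favours the device.

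The omission is not a habit of the SAP. Withdrawal is part of the rule for the balloon in the same section, and part of the rule for the stent system in SAP 8.5.1. Only the sheath loses it.

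At stake is the accuracy of one of the two secondary efficacy endpoints. The primary objective names the sheath as part of the system under evaluation.

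**Working it through.** **No figure to reproduce.** The documents give no rate, sample size or power for this endpoint. The check is a comparison of texts, followed by an illustration of size.

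**Step 1: set the rules side by side.**

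| Source | Insertion | Withdrawal | Unit |
|---|---|---|---|
| SAP 4.2 and Protocol 8.2 (definition) | required | required | not stated |
| SAP 8.5.2, counting sentence | required | absent | sheaths |
| SAP 8.5.2, preceding sentence | – | – | subjects |
| Protocol 14.4.2 | – | – | subjects |
| SAP 12, Table 1 | no row for this endpoint | no row | – |

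Nothing after the counting sentence brings withdrawal back.

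**Step 2: direction of the error.** Take n subjects with one attempted sheath each. Let i be the number not successfully inserted, and w the number inserted but not successfully withdrawn.

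- As written: (n − i)/n
- As defined: (n − i − w)/n
- Difference: w/n, which is never negative

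**Step 3: illustration.** The inputs are n = 129 (SAP 5, study sample size) and three assumptions: one sheath per subject, i = 0, and w from 0 to 3. The two-sided 95% Clopper-Pearson limits for x successes in n are the 0.025 quantile of Beta(x, n − x + 1) and the 0.975 quantile of Beta(x + 1, n − x). When x = n the upper limit is 1 and the lower limit is 0.025^(1/129) = 0.972.

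| w | As written (95% CI) | As defined (95% CI) |
|---|---|---|
| 0 | 129/129 = 100% (97.2–100) | 129/129 = 100% (97.2–100) |
| 1 | 129/129 = 100% (97.2–100) | 128/129 = 99.2% (95.8–99.98) |
| 2 | 129/129 = 100% (97.2–100) | 127/129 = 98.4% (94.5–99.8) |
| 3 | 129/129 = 100% (97.2–100) | 126/129 = 97.7% (93.4–99.5) |

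Each withdrawal failure costs 1/129, or about 0.8 of a percentage point. The largest gap in the table is 100 − 97.7 = 2.3 points.

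**Step 4: does the unit matter?** With one sheath per subject, counting sheaths and counting subjects give the same fraction. Suppose instead that one subject has a failed first insertion and a successful second sheath. The sheath count gives 129/130 = 99.2% (95.8–99.98). Per subject, the result is 128/129 = 99.2% (95.8–99.98) if every attempted sheath must succeed, or 129/129 = 100% (97.2–100) if one success is enough. Moving from sheaths to subjects hardly changes the figure by itself. The scoring convention can, and none is stated.

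**The case against.** **The sentence may be only shorthand.** SAP 8.5.2 says that the ratio estimates technical success, a term that SAP 4.2 defines with withdrawal included, and it does not claim to redefine it. SAP 6 gives the population and SAP 8.1 the general form of a rate with an exact interval. An analyst could build the right calculation from these. This stands in part: the correct definition is in the same document, and a careful analyst may apply it. But the SAP then holds two instructions for one number, and the more specific one is incomplete.

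**The unit mismatch is not a second error of substance.** A reader might infer that counting sheaths under a per-subject heading distorts the result. The documents do not support that. Protocol 11.1 is written for one sheath, placed in step 3 and removed in step 7, and the stated reason for the per-subject unit is that the sheath stays in place between lesions. A second sheath is not ruled out (Protocol 2.2 lists two lengths), but none is described. This objection stands.

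**Withdrawal failures would not be hidden.** This also stands for malfunctions. Under Protocol 13.6, "A device malfunction is considered a failure of a device to meet any of its performance specifications or otherwise perform as intended". That section speaks of investigational devices and the sheath is CE marked, but Protocol 13.7 applies the same criteria to CE marked products. A withdrawal malfunction would therefore appear in the sheath deficiency rows of Table 1. That makes the event visible; it does not correct the success rate.

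**Conclusion.** The point holds as an error in the stated calculation. SAP 8.5.2 omits a required component of the endpoint, and the resulting rate can only equal or exceed the defined one when both are scored on the same unit. Under the assumptions above, the overstatement is 0.8 of a point with one withdrawal failure and 2.3 points with three. If no withdrawal fails, it is zero. The failure counts are assumed for illustration and say nothing about how often withdrawal will fail.

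Severity is minor. A reader might infer that the trial's success decision is affected, and it is not. This endpoint carries no hypothesis test. The primary efficacy analysis concerns the stent system and has its own rule, which includes withdrawal. Both primary tests, the sample size and the definition of trial success stand unchanged.

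**What to change.** In SAP 8.5.2, replace the counting sentence with this rule: the numerator is the number of subjects who meet the full Section 4.2 definition, that is, successful insertion and successful withdrawal of the BRITE TIP RADIANT sheath; the denominator is the number of subjects with at least one attempted BRITE TIP RADIANT insertion. Keep the two-sided 95% Clopper-Pearson interval. This restores the defined endpoint and matches the per-subject unit already stated in SAP 8.5.2 and Protocol 14.4.2.

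Optionally, the sponsor may state how a subject with more than one attempted sheath is scored. That choice is the sponsor's and is separate from the error.

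The cost is one sentence of SAP text, with no change to the endpoint, sample size or primary tests. It assumes that sheath withdrawal is already recorded, as the protocol endpoint requires; the case report form is not among the documents, so this should be confirmed.

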## 8.6 Adverse Events

In addition to the adverse event rates estimated for the secondary safety endpoint, all adverse events (AE), serious adverse events (SAE), major adverse events (MAE), and unanticipated adverse device effects (UADE) will be tabulated (or listed). The table or listing will contain the term or description, start and end dates, severity, outcome, and causality or association to the investigational product or procedures. These summary tables will present descriptive statistics. No formal testing will be done.

## 8.7 Additional Endpoints

The additional data points of fluoroscopy time, procedural time, time to achieve hemostasis, time to ambulation, time to hospital discharge, time to hospital discharge eligibility, method to achieve closure, and the scoring of the EQ-5D and SF-36 will be completed on a per subject basis.

Estimates of each of the endpoints related to time will be summarized with a mean, standard deviation, median, and a range expressed as a minimum and maximum. For each estimate, a two-sided 95% confidence interval will be calculated using normal approximation methods.

The method of vascular closure will be reported as the percent of subjects falling into closure categories.

The EQ-5D will be reported as the proportion of subjects falling within the scale for each domain at three time points; Screening, Discharge, and 30 day follow-up. Each domain is a rank-order scale in which lower numbers represent outcomes superior to those represented by higher numbers (i.e. "1" is best and "5" is worst) for each time point. Overall health score, however, is reported as a mean and standard deviation at each time point. For the SF-36, results within each subscale will be summarized with a mean and standard deviation at three time points: screening, discharge and 30-day follow-up.

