8.4 Rationale for Study Endpoints

Each of the primary and secondary safety and/or efficacy endpoints above aligns with the primary objective of the study in evaluating acute safety and efficacy of the S.M.A.R.T. RADIANT™ Vascular Stent System,

RADIANT / P21-7701

Version: 7.0 / March 21, 2023

when used with the BRITE TIP RADIANT™ Guiding Sheath and SABERX RADIANT™ PTA Balloon Catheter in treating femoropoliteal or iliac artery lesions via a radial artery approach.

Regarding the S.M.A.R.T. RADIANT device in particular: since the investigational S.M.A.R.T. RADIANT delivery system incorporates the CE marked S.M.A.R.T. stent, for which there is an abundance of short-term and long-term clinical data available from its evaluation in previous, Cordis-sponsored studies, the main purpose of this study is to assess the safety and performance (outcomes) of the delivery system versus the stent. There is proven, long-term primary patency through 10 years and low stent fracture rate through 3 years following implantation of the S.M.A.R.T. stent. Therefore, rates of vessel patency, restenosis, stent fractures, etc. have not been included as pre-specified endpoints for this study.

The various health economic endpoints will be used to determine if there are cost savings/benefits, such as decreased procedural/treatment and hospitalization costs, for patients who are eligible for and undergo procedures that can be completed via a transradial versus transfemoral arterial approach. General and disease-specific outcomes assessed via the SF-36 and EQ-5D standarized, validated questionnaires will help determine if there is overall, improved quality-of-life in the short-term in patients that undergo stenting procedures via transradial approach to 30 days post-procedure.

9 Informed Consent

Prior to enrollment and performance of any study-specific activities or procedures, the study team shall:

1. Provide each prospective subject with a full explanation of the study (including all potential benefits and risks) that is also documented (i.e., informed consent form) and ensure they have understood all information that has been presented to them.
 - a. The informed consent form (ICF) should enable the subject to understand:
 - i. the nature, objectives, benefits, implications, risks and inconveniences of the clinical investigation;

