11.3 Treatment Failures

In the event of a device deficiency, detailed information on the product, circumstances of the deficiency as well as any complications and their management will be collected and reported to the sponsor, as described in Section 13.6.

RADIANT / P21-7701

Version: 7.0 / March 21, 2023

Failure to implant the assigned study device will be recorded on the CRF as a treatment failure. In the event of a treatment failure, each site will follow their standard-of-care procedures (and/or use commercially-available products) to ensure the safety of the subject.

Any subject enrolled in this clinical study that does not receive the study device (S.M.A.R.T. stent) will be followed to 30 days post-procedure to be monitored for safety (adverse events and overall health) but will not be required to complete any of the study-specific procedures/assessments scheduled for the 30-day follow-up visit. If applicable, the Investigator must return any malfunctioned/damaged/unused investigational devices to the sponsor or its designee in accordance with the instructions provided.

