Rate of SaberX Radianz PTA Balloon Catheter Deficiencies Roll-in Subjects Only	Two-sided Exact 95% Confidence Interval (one or more per procedure, w/wo)	Exploratory				X
Rate of S.M.A.R.T Radianz Vascular Stent System Deficiencies Non-Roll-in Subjects	Two-sided Exact 95% Confidence Interval (one or more per procedure, w/wo)	Exploratory			X	
Rate of S.M.A.R.T Radianz Vascular Stent System Deficiencies Roll-in Subjects Only	Two-sided Exact 95% Confidence Interval (one or more per procedure, w/wo)	Exploratory				X
Subgroup analysis for Secondary Safety Variables by Gender and Lesion Type (Iliac and Femoral/Popliteal)	Two-sided Exact 95% Confidence Interval (one or more per procedure, w/wo)	Exploratory			X	X
Rate of AEs; Run Separately for Non-Roll-in and Roll-in Subjects	Two-sided Exact 95% Confidence Interval (one or more per procedure)	Exploratory			X	X
Rate of Death	Two-sided Exact 95% Confidence Interval (one or more per procedure)	Exploratory			X	X
Rate of Index Limb Amputation	Two-sided Exact 95% Confidence Interval (one or more per procedure)	Exploratory			X	X
Rate of Target Lesion Revascularization	Two-sided Exact 95% Confidence Interval (one or more per procedure)	Exploratory			X	X
Rate of Procedural Complications, Separately for Non-Roll-in and Roll-in Cohorts	Two-sided Exact 95% Confidence Interval (one or more per procedure)	Exploratory			X	X
Additional Variables						
Fluoroscopy Time	Mean, 95% CI	Exploratory			X	X
Procedure Time	Mean, 95% CI	Exploratory			X	X
Time to Hospital Discharge, Minutes	Mean, 95% CI	Exploratory			X	X

Time to Hospital Discharge Eligibility, Minutes	Mean, 95% CI	Exploratory			X	X
Method of Transradial Artery Access Site Closure	Tabulation with Percentages	Exploratory			X	X
SF-36 Subscale Results	Mean, Standard Deviation and 95% CI for Each Domain	Exploratory			X	X
EQ-5D Subscale Results	Tabulations by Dimensions with Percentages for Each Domain	Exploratory			X	X
Descriptive Statistics-Age/Gender/Lesion Type (Mean, SD, Median, Min and Max or Tabulation for Categorical Variables)	Run Poolability Analysis Separately by Site	Exploratory			X	X

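### The protocol asks whether quality of life improves to 30 days, but the SAP summarises each visit separately and plans no estimate or interval for within-subject change

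*SAP*

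**What the plan says.** **The question.** Protocol 8.4 gives the purpose of SF-36 and EQ-5D: they are to "help determine if there is overall, improved quality-of-life in the short-term in patients that undergo stenting procedures via transradial approach to 30 days post-procedure".

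**The data.** The time and event schedule (Protocol Table 1) has both questionnaires at screening, discharge and 30 days. Protocol 8.3 says they are given to all subjects. SAP 8.1 defines a baseline for each parameter as the last value before treatment.

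**The planned summaries.**
- SF-36, SAP 8.7: "results within each subscale will be summarized with a mean and standard deviation at three time points", the three being screening, discharge and 30 days.
- SF-36, SAP Table 1 (section 12): "Mean, Standard Deviation and 95% CI for Each Domain", marked exploratory.
- EQ-5D domains, SAP 8.7: "The EQ-5D will be reported as the proportion of subjects falling within the scale for each domain at three time points".
- EQ-5D overall score, SAP 8.7: "Overall health score, however, is reported as a mean and standard deviation at each time point".

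**Who is measured at 30 days.** Under Protocol 11.3, an enrolled subject who does not receive the stent "will not be required to complete any of the study-specific procedures/assessments scheduled for the 30-day follow-up visit". Protocol 11.10 says early exits are not replaced. The missing-data sections (Protocol 14.5, SAP 11) give rules for the primary endpoints and, in the protocol, the secondary endpoints. Neither gives one for quality of life, which both documents class as an additional data point.

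**The concern.** In a single-arm study, improvement can only mean change from the subject's own earlier value. The plan collects that value and defines a baseline, but no quality-of-life output uses either. The final tables would show three sets of means, SDs and proportions, and the reader would have to compare them by eye.

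Two things are lost. First, a mean and SD per visit do not carry the correlation between a subject's two scores, so the interval for the mean change cannot be recovered. Likewise, unchanged EQ-5D domain proportions could mean that nobody moved, or that as many subjects worsened as improved. Second, each visit's summary rests on whoever answered at that visit, so a difference between visit means can partly reflect who is missing.

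What is at stake is the readability of an exploratory result, not the trial's conclusion.

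**Working it through.** **Source of n.** The documents state no SD, correlation, effect size or precision for quality of life. The only design figure behind the sample size is the 88% power of the primary tests, and it reproduces. With 129 limbs, the smallest count whose one-sided 95% Clopper-Pearson lower bound exceeds 0.93 is 125 (bound 0.9305). The exact alpha is 0.0481, and power at a true rate of 0.98 is 0.882. This confirms the n used below and says nothing about quality of life.

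**Precision.** Inputs: n = 129 (SAP 5); equal SD at the two visits (assumption); within-subject correlation r (assumption, shown as a range). Half-widths are in SD units.

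- Two visit means treated as independent: 1.96 × √(2/n) = 1.96 × √(2/129) = 0.244.
- Paired change: 1.96 × √(2(1 − r)/n).
- Ratio of the first to the second: 1/√(1 − r).

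| Assumed r | Paired half-width | Independent half-width | Ratio |
|---|---|---|---|
| 0 | 0.244 | 0.244 | 1.00 |
| 0.3 | 0.204 | 0.244 | 1.20 |
| 0.5 | 0.173 | 0.244 | 1.41 |
| 0.7 | 0.134 | 0.244 | 1.83 |

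The gain disappears at r = 0 and grows with r. The half-width around a single visit mean, closest to what SAP Table 1 plans for SF-36, is 1.96 × √(1/129) = 0.173 SD. That interval describes the level at one visit, and it equals the paired-change interval only at r = 0.5.

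**Allowing for missing 30-day values.** With 126 pairs the paired half-widths at r = 0.3, 0.5 and 0.7 are 0.207, 0.175 and 0.135. With 116 pairs (an assumed 10% missing) they are 0.215, 0.182 and 0.141, against 0.251 for 129 and 116 treated as independent.

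**Effect of who is measured.** If a fraction m lacks 30-day data and their screening scores differ from the others by an assumed 0.5 SD, the difference between visit means shifts by m × 0.5 SD.

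- At the assumed 98% success: 0.02 × 129 = 2.6, about 3 subjects. The shift is 3/129 × 0.5 = 0.012 SD.
- At the 93% performance goal: 0.07 × 129 = 9.03, about 9 subjects. The shift is 9/129 × 0.5 = 0.035 SD.
- At an assumed 10% missing for any reason: 13 subjects. The shift is 13/129 × 0.5 = 0.050 SD.

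The first two counts are approximate. The success rate is per limb, and not every technical failure means that no stent was received.

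**The case against.** The strongest reply is that little depends on this. Quality of life is neither a primary nor a secondary endpoint, nothing is tested, and trial success rests on the two primary endpoints alone. Protocol 8.4 says only that the questionnaires will help determine improvement. With one arm, even a precise change could not be attributed to transradial access. The data are kept, so change can still be computed later. Extra intervals for every subscale at two visits also add unadjusted comparisons to an uncontrolled dataset. All of this stands. It limits the importance of the point but does not supply the missing estimate.

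Four stronger readings are tempting, and the documents do not support them:

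- A reader might infer that each visit describes different subjects. It is one cohort, assessed at all three visits, with Protocol 11.7 allowing remote collection at 30 days in exceptional circumstances. The sets overlap and may shrink.
- A reader might infer that all technical failures are excused from the 30-day questionnaires. Protocol 11.3 excuses only subjects who do not receive the stent. A stent deployed away from the intended location is a technical failure, but that subject received it and is not excused.
- A reader might infer that the plan answers the question with an interval that is too wide. It plans no interval for change at all. The 0.244 SD is what a reader would obtain by treating the visits as independent.
- A reader might infer that pairing removes bias from missing data. It puts the same subjects on both sides of the comparison, but selection among completers remains.

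**Conclusion.** The point holds as a low-cost improvement. The protocol states an interest in improvement to 30 days, and neither document plans a change score, a paired interval or a table of shifts between levels. Subtracting visit means gives a rough point estimate on sets that may not match, and no valid interval for change can be built from the planned summaries.

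At n = 129, treating the visits as independent gives a 95% half-width of 0.244 SD, against 0.204 to 0.134 SD for the paired change. This rests on equal SDs and on assumed correlations of 0.3 to 0.7. The shift from who is missing is the minor part: about 0.01 SD at the assumed 98% success rate, if those without a 30-day value differ at screening by an assumed 0.5 SD, and about 0.05 SD if 10% are missing. Trial success and the sample size are unaffected.

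**What to change.** In SAP 8.7 and SAP Table 1:

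- For each SF-36 subscale and the EQ-5D overall health score, add the mean change from screening to discharge and from screening to 30 days, with SD, paired 95% CI and number of pairs, in subjects with both values.
- For each EQ-5D domain, report the numbers improved, the same and worse at discharge and at 30 days relative to screening.
- Report screening scores separately for subjects with and without 30-day data, so that selection among completers is visible.
- Keep the visit summaries as descriptive. Label all of these outputs exploratory and state that the intervals are not adjusted for multiplicity.

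The cost is a few lines of SAP text and some programming. No new data, visits or subjects are needed. The drawback is a larger number of unadjusted exploratory intervals, which the labelling addresses.
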